2.2 Secondary Objectives

Secondary objectives are to compare motor and non-motor symptoms, quality of life, and daily functioning, adverse effects and complications between treatment with DBS and CLI.

Version 7: 23-10-2019 12 of 48

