8.8 Secondary study parameter(s)

RCT

The main clinical analysis of the study consists of a comparison between the trial treatment groups (DBS versus CLI) of the primary clinical outcome (PDQ-39) 12 months after the start of the study treatment. First, the follow-up difference between PDQ-39 scores will be analysed using a two-group t-test. Second, the PDQ-39 follow-up scores will be further investigated using multiple linear regression taking into account patients' PDQ-39 baseline values, the stratifying variables (experience of the including centre with DBS and CLI; response to Levodopa) and (if necessary) for clinically relevant baseline imbalances. Additionally, the repeated data structure will be investigated with a linear mixed model. The same analyses will be performed for the 24 and 36 month outcomes. With regard to the comparisons of the other secondary outcomes PD motor symptoms (MDS-UPDRS, CDRS, 3-day motor symptom diary), non-motor symptoms such as autonomic functions and sleep (Non Motor Symptom Checklist, Rotterdam Symptom Checklist), PD-medication, neuropsychological and psychiatric assessment, disability, functional health status (ALDS), patient and physician preferences, patient satisfaction, adverse effects and complications, treatment failure, stopping treatment, starting with the alternative than initially started treatment, caregiver burden and medical and non-medical care costs (iMCQ, iPCQ) we will use the appropriate parametric and non-parametric statistics. In all analyses, statistical uncertainties will be expressed in 95% confidence intervals.

Patient preference trial

As mentioned before a patient preference observational study will be conducted to asses external validity of the randomized controlled trial results. The primary clinical outcome of the non-randomized group and randomized group will be compared using the two-group t-test and linear regression, whereas baseline characteristics will be compared with the

Version 7: 23-10-2019 32 of 48

two-group t-test and Chi-square test, when appropriate. Finally, the impact of the treatment on the PDQ-39 follow-up scores of the randomized and non-randomized group will be analysed using multiple linear regression, adjusting for relevant imbalanced baseline variables and randomized status (agreeing to randomization or not).

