The difference between both treatment groups in the mean change from baseline to 12 months in total MDS-UPDRS part II and III was shown with 95% CI. Similarly, the difference between groups in mean change from baseline to 12 months in CDRS was shown, as well as the difference in mean change in total time in both off-drug state and on-drug state without bothersome dyskinesias as reported in the 3-day motor diary, the difference in mean change in usage of dopaminergic medication (LEDD), and ALDS in on-drug phase, all with 95% CI. Discontinuation of the allocated treatment or switch to the other treatment option were summarized using simple descriptive statistics. The change in cognition expressed in points on PD-CRS from baseline to 12 months was reported. For apathy, the numbers and frequencies of patients with apathy at baseline and after 12 months follow-up were shown. Moreover, the numbers and frequencies of patients who had developed apathy after 12 months (*i.e.*, no apathy at baseline, but presence of apathy after 12 months), was reported for both groups, including the difference between these frequencies and 95% CI. Similarly, numbers and frequencies of impulsive-compulsive disorders and, separately, of development of impulsive-compulsive disorders were shown, with difference and 95% CI of the latter. Additionally, the numbers and frequencies of resolution of impulse control disorders were reported for both groups as well as the difference and 95% CI. Psychiatric diagnoses were reported analogues to impulse-compulsive disorders.

The number of patients that would recommend their treatment at 12 months to others was reported and the difference in frequency between the treatment groups was reported with 95% CI.

We presented line listing of safety outcomes using counts and percentages. All (S)AEs, including death were reported for each treatment arm. See Table SAP3 for an overview of (S)AEs. The treatment course per group was expressed in number of patients stopping allocated treatment and number of patients switching to the alternative treatment.

Table SAP2. Main and secondary clinical outcomes at 12 months, mITT RCT population

Part A: continuous outcomes

Outcome	Within-treatment Change from Baseline to 12 Months								Between-Group Difference in Change from Baseline mean (95% CI)	P-value
	Baseline				Months					
	CLI		DBS		CLI		DBS			
no. of patients	mean ±SE	no. of patients	mean ±SE	no. of patients	mean ±SE	no. of patients	mean ±SE			

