Main clinical outcome										
PDQ-39 summary index score										P
Secondary clinical outcomes										
MDS-UPDR-III score in on-phase										NR
CDRS in on-phase										NR
Time in on-phase without troublesome dyskinesias (hr)										NR
Time in off-phase (hr)										NR
LEDD (mg per day)										NR
ALDS score in on-phase										NR
PD-CRS score										NR

ALDS: Amsterdam Linear Disability Scale, CDRS: Clinical Dyskinesia Rating Scale, CI: confidence interval, CLI: continuous intrajejunal levodopa infusion, DBS: deep brain stimulation, hr: hours, LEDD: Levodopa Equivalent Daily Dose, MDS-UPDRS: Movement Disorder Society's Unified Parkinson's Disease Rating Scale, mg: milligrams, NR: not reported, PD-CRS: Parkinson's Disease Cognitive Rating Scale, PDQ-39: Parkinson's Disease Questionnaire-39, SE: standard error

Table 2. Main and secondary clinical outcomes at 12 months, mITT RCT population
Part B: dichotomous outcomes

Outcome	Baseline		12 Months		Between-group Difference at 12 months	Development / resolution *		Between-group Difference in development / resolution*
	CLI	DBS	CLI	DBS	difference in proportion (95% CI)	CLI	DBS	difference in proportion (95% CI)
	n/total no. of patients (%)	n/total no. of patients (%)	n/total no. of patients (%)	n/total no. of patients (%)		n/total no. of patients (%)	n/total no. of patients (%)	
Apathy (SAS)								
Impulsive-compulsive disorder (QUIP)								
Psychiatric diagnosis (MINI)								
Patient would recommend treatment	-	-				-	-	-

CLI: continuous intrajejunal levodopa infusion, DBS: deep brain stimulation, MINI: Mini International Neuropsychiatric Interview, NA: Not applicable, NR: not reported, SAS: Starkstein Apathy Scale, SE: standard error, QUIP: Questionnaire for Impulsive-Compulsive Disorders in Parkinson's Disease

* the first number relates to development of the outcome, the second number relates to resolution of the outcome (if applicable)

Table SAP3. (Serious) Adverse Events

	CLI- RCT (n)	DBS-RCT (n)	CLI-observational (n)	DBS-observational (n)
Serious Adverse events				
Death (n,%)				
Related to therapy (n,%)				
Other causes (specified, n,%)				
Hospital admission (n,%)				
Related to therapy (n,%)				
Other reason (specified n,%)				
Other SAEs (n,%)				
Specified (n,%)				
Adverse events				
Gastro-intestinal related (n,%)				
Specified (n,%)				
Polyneuropathy (n,%)				
Cerebral hemorrhage (n,%)				
Related to therapy (n,%)				
Epilepsy (n,%)				
Other (n,%)				
Specified (n,%)				

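### The SAP plans no between-arm difference or 95% CI for adverse events, stopping or switching, although the protocol lists them among its comparisons and asks for intervals in all analyses

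*SAP*

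**What the plan says.** **Protocol.** The secondary objectives in 2.2 include comparing "adverse effects and complications between treatment with DBS and CLI". Section 8.8 lists adverse effects and complications, stopping treatment and starting the alternative treatment among the secondary outcomes to be compared with suitable parametric or non-parametric methods. It closes that list with: "In all analyses, statistical uncertainties will be expressed in 95% confidence intervals". Section 7.5 says that numbers stopping and crossing over will be recorded and ranks them as important secondary outcomes.

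**SAP.** Harms and treatment course are both listed as secondary outcomes of the randomized trial. The General principles section says that uncertainty is expressed in two-sided 95% intervals, and that no individual P-values are reported beyond the main clinical outcome. Under Analysis of secondary clinical outcomes, however, the plan for safety is: "We presented line listing of safety outcomes using counts and percentages", followed by "All (S)AEs, including death were reported for each treatment arm". For treatment course it is: "Discontinuation of the allocated treatment or switch to the other treatment option were summarized using simple descriptive statistics", and later: "The treatment course per group was expressed in number of patients stopping allocated treatment and number of patients switching to the alternative treatment".

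Table SAP3 has four group columns (two randomized, two observational) and rows marked n and %. It has no difference column, no interval column, and no row for patients with at least one SAE or AE. Stopping and switching have no row in Table SAP2 Part B.

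**The concern.** Harm is part of the question this trial asks. The hypothesis in the protocol summary weighs the extra cost of CLI against quality of life, symptoms and adverse events, and the introduction says that little is known about how the two adverse-effect profiles compare. A randomized contrast is therefore one of the useful things the trial can deliver.

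With about 26 to 33 patients per arm, two bare percentages can be misread either way. A gap may look like evidence that one therapy is safer, and similar figures may look like evidence that they are equally safe. An interval shows how little either reading is supported. Adverse events carry a second problem: rows by type may overlap within a patient, so a reader cannot add them up to the share of patients affected.

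**Working it through.** **1. Protocol and SAP side by side**

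| Outcome | Protocol basis for a comparison | Counted in patients in the SAP? | Difference with 95% CI in the SAP? |
|---|---|---|---|
| Adverse events, SAEs | 2.2, 8.8 | Not stated | No |
| Stopping | 7.1.2, 7.5, 8.8 | Yes | No |
| Switching | 7.1.2, 7.5, 8.8 | Yes | No |
| Apathy, impulsive-compulsive disorder, psychiatric diagnosis, recommending treatment | Not needed for this point | Yes | Yes (Table SAP2 Part B) |

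The last row shows that the SAP already has a way to report a binary outcome with a difference and interval and no P-value. It is not used for the first three rows. The SAP's account of protocol development explains changes to the strata, the repeated measures and the analysis population, but does not mention this one.

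**2. Arm sizes**

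The documents give no planning rate, power or precision for harms, so there is no stated figure for this point to reproduce. The arm sizes are the only planning inputs. From protocol 4.4:

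- SD of net health benefit = √(0.35² + (10,000/120,000)²) = 0.360
- n per group = 2 × (1.96 + 0.842)² × 0.360² / 0.2847² ≈ 25.1, rounded up to 26
- 26 / 0.8 = 32.5, rounded up to 33 per group, 66 in total

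Both match the protocol.

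**3. Precision of a risk difference at those sizes (assumed rates)**

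Half-width = 1.96 × √[p₁(1−p₁)/n + p₂(1−p₂)/n].

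| Assumed rates | n = 26 per arm | n = 33 per arm |
|---|---|---|
| 10% v 10% | ±16.3 points | ±14.5 points |
| 30% v 10% | ±21.1 points | ±18.7 points |
| 50% v 50% | ±27.2 points | ±24.1 points |

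**4. Worked example (assumed counts), Newcombe interval**

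With Wilson limits (l, u) for each arm, the lower limit is d − √[(p₁−l₁)² + (u₂−p₂)²] and the upper limit is d + √[(u₁−p₁)² + (p₂−l₂)²].

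- 8/26: p₁ = 0.308, Wilson limits 0.165 to 0.500
- 4/26: p₂ = 0.154, Wilson limits 0.062 to 0.335
- d = 0.154
- Lower: 0.154 − √(0.143² + 0.181²) = −0.077
- Upper: 0.154 + √(0.192² + 0.092²) = 0.367

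The difference is 15 points, 95% CI −8 to 37. The same formula for 10/33 versus 5/33 gives 15 points, −5 to 34.

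**The case against.** The strongest defence is that descriptive safety tables are common in small trials. Protocol 8.8 names no method for adverse events, and the SAP's general statement on intervals could be read as covering them. On that reading this is a mismatch between a principle and a table shell, and not a decision to drop intervals. That is fair as to intent: the documents do not show a deliberate choice. It does not close the gap, because the specific wording and the table shell are what will be carried out. Low power for harms is a reason to show an interval.

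It can also be said that little is lost. Stopping and switching are counted in patients, and a flow diagram is planned, so a reader could compute those intervals. That stands for treatment course. For adverse events it holds only if the line listing is by patient, which the SAP does not say.

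A reader might be tempted by stronger claims that the documents do not support:

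- That safety is reported as counts alone. The SAP says counts and percentages.
- That no patient-level figure exists for any of these outcomes. Stopping and switching are numbers of patients; the gap concerns adverse events only.
- That protocol 2.2 makes stopping and switching part of the secondary objective. It names adverse effects and complications; the basis for the others is 7.1.2, 7.5 and 8.8.
- That the secondary objective gets no estimate. Section 2.2 also covers symptoms, quality of life and daily functioning, and the SAP plans differences with intervals for many of these, including apathy, impulsive-compulsive disorder and psychiatric diagnoses.
- That patients are known to be counted in several rows of Table SAP3. This is plausible, but the table does not state its counting unit, and that omission is itself the defect.

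**Conclusion.** The point holds as a minor one. For adverse events, stopping and switching, the SAP plans per-arm summaries without a contrast or its precision, against protocol 8.8 and the SAP's own principle. For adverse events it also leaves the proportion of patients affected underivable from Table SAP3.

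On size, at the planned numbers a 95% interval for a risk difference would run roughly ±14 to ±24 points with 33 per arm and ±16 to ±27 points with 26 per arm. These figures assume event rates of 10% to 50%, because the documents give none. The arm sizes are planning figures; the SAP reports that several patients refused CLI straight after allocation, so the analysed CLI arm may be smaller and its intervals wider. The figures show what the planned tables leave out. They say nothing about which therapy is safer.

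**What to change.** For the two randomized arms:

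- Add rows to Table SAP3 for patients with at least one SAE, at least one therapy-related SAE and at least one AE, with the number of events beside each.
- State the counting unit and the denominator. The mITT population fits, because the SAP defines switching as occurring after the allocated treatment was first received. Report immediate refusals after randomization separately, so that they are neither lost nor mixed with later switches.
- For these rows and for stopping and switching, report the CLI minus DBS difference in proportions with a 95% Newcombe interval and no P-value.
- Use a simple layout of n/N (%) per arm plus difference (95% CI). The Part B shell of Table SAP2 cannot be copied unchanged, because its baseline and development/resolution columns do not apply here.

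The cost is a few table rows and one named interval method, with no new data. The downside is that the intervals will be wide, and the text should say so.

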8.2 AEs, SAEs and SUSARs

8.2.1 Adverse events (AEs)

Adverse events are defined as any undesirable experience occurring to a subject during the study, whether or not considered related to the experimental intervention or the investigational product. All adverse events reported spontaneously by the subject or observed by the investigator or his staff will be recorded in patients participating in the randomised controlled trial, from the moment patients undergo visit 1: screening until end of study. Since the patient preference study is observational, adverse events and SAEs will be reported using line listing.

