Originally, an intention-to-treat analysis (ITT) was planned as the primary analysis. Nevertheless, during the study it was observed that after allocation, several patients immediately refused CLI treatment and either chose to be treated with DBS or quitted study participation. Analyzing these patients in an ITT could have introduced a significant bias, as their apparent preference for DBS made them not representative of a population that considered CLI a suitable treatment for advanced PD. Furthermore, for the patients for whom post-baseline data were not available, all these data would have had to be imputed, contributing to the risk of bias. A modified intention-to-treat (mITT) population was introduced as the primary analysis, because analysis in the ITT population including all randomized individuals was considered less valid.⁷ The mITT population included all randomized patients who received the allocated treatment and continued in the RCT after randomization. Additionally, in line with the proposed strategy for ITT analyses for trials with incomplete outcome data as proposed by White et al.,⁷ sensitivity analyses were performed to explore the robustness of the main analyses in the mITT population and included analyses in all randomized patients (the ITT population). Please see “Sensitivity analysis” for details on page 12.

While conducting the study, it was observed that comorbidities had a negative impact on completeness of the follow-up data. To assess for a possible bias towards a selective data collection of healthier patients, treating physicians of patients that had dropped out of the study were contacted to obtain additional information on the general health status and level of functioning of these patients. Please see also “Patient replacement and missing data” on page 10.

Study methods

Outcomes - randomized controlled trial

Primary outcomes

The main clinical outcome was the change from baseline to 12 months after initiation of treatment in PDQ-39 (score 0-100).⁸

The primary health economic outcomes are elaborated on page 19.

Secondary outcomes

- PD motor symptoms -- Movement Disorder Society’s Unified Parkinson’s Disease Rating Scale (MDS-UPDRS) part III in on-drug state (score range 0-132) ²;
- Motor experiences of daily living-- MDS-UPDRS part II in on-drug phase (score range 0-52) ²;
- Dyskinesia -- Clinical Dyskinesia Rating Scale (CDRS, score range 0-28) in on-drug state ⁹;

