According to the Consolidated Standards of Reporting Trials 2010 statement (CONSORT), a flow diagram illustrating the number of participants ineligible, eligible, consented, randomized, received allocated treatment, excluded, withdrawn and lost to follow-up for the primary outcome was provided. Please see the Figure SAP-1 on page 29.

Analysis populations

Modified intention-to-treat population

The primary analysis consisted of the modified intention-to-treat (mITT) population which included all randomized patients who received the allocated treatment, regardless of continuation of treatment. Analyses in the original ITT population including all randomized patients, regardless of the treatment they had actually received (*i.e.*, also patients not receiving the allocated treatment and patients quitting study participation immediately after randomization) were accounted for in sensitivity analyses (see page 12, “Sensitivity analysis”) and were presented in the supplements.

As-treated population

To provide insight in potential bias resulting from excluding patients who did not adhere to the allocated treatment or switched treatment, analyses were additionally performed in an as-treated population categorizing the randomized patients according to the actual treatment(s) they were receiving at the moment of the 12-month visit (if available).⁷

Per protocol population

The per protocol population consisted of all patients receiving the allocated treatment who completed the study protocol without protocol violations.

Ancillary patient preference population

The ancillary patient preference population consisted of all patients who signed informed consent for this element of the study, started the chosen treatment and underwent at least the baseline visit and one follow-up visit. Patients were allowed to participate in the ancillary patient preference cohort study after withdrawal of consent for the RCT prior to randomization. Please see also Appendix II for the flowchart of the Ancillary patient preference cohort.

Adherence and protocol deviations and violations

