For other clinical outcomes at 12 months, the last observation was carried forward if available from another visit (excluding baseline). For baseline characteristics, missing values were not imputed. For displaying baseline characteristics, the numerator and denominator were stated for dichotomous

variables (e.g., male: 5/15). For continuous variables, the number of patients for whom the variable was available was stated.

Study population

Baseline characteristics

For both the RCT mITT population and for the ancillary patient preference population, baseline characteristics were presented in Table SAP1. Categorical baseline characteristics were summarized by presenting counts and percentages. Visual inspection was used for assessment of normality of data distributions. Continuous, normally distributed variables were summarized by presenting the means and standard deviations. Continuous, non-normally distributed and ordinal variables were summarized by presenting the medians and interquartile ranges. Formal statistical tests were not performed to examine baseline differences between treatment groups. No bootstrapping was used for presentation of the baseline characteristics.

Table SAP1. Baseline characteristics

	CLI-RCT (n)	DBS-RCT (n)	CLI- observational (n)	DBS- observational (n)
Age (years)				
Sex, F (% n/N)				
Time since PD diagnosis (years)				
Hoehn and Yahr stage in on-drug state				
Levodopa-equivalent daily dose (mg/day)				
MDS-UPDRS part III score			NA	NA
- off-drug state				
- on-drug state				
- improvement off- to on-phase (%)*				
Parkinson's disease cognitive rating score			NA	NA
Level of experience of treating center with CLI and DBS treatment (%)**				
- Experienced in CLI, not in DBS				
- Experienced in DBS, not in CLI				
- Experienced in both CLI and DBS				
- Little experience in both CLI and DBS				

CLI: continuous intrajejunal levodopa infusion, DBS: deep brain stimulation, F: female, MDS-UPDRS: Movement Disorder Society's Unified Parkinson's Disease Rating Scale, mg: milligrams, NA: not available, RCT: randomized controlled trial

** Improvement: (score in off-drug state minus score in on-drug state) divided by score in off-drug state*

***Experienced in DBS/CLI: ≥ 5 patients treated per year in the two years previous to including the patient with the respective treatment in the treating center. A center may have changed in level of experience over time.*

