For normally distributed data means and standard deviation were presented, for non-normally distributed data medians and interquartile ranges. For the Hoehn & Yahr stage median and range were reported.

Analyses

Randomized controlled trial

Reported outcomes were presented in Table SAP2 (part A and B). The main publication consisted of analyses in the mITT population. The analyses in ITT, as-treated and per-protocol populations were presented in supplements.

Analysis of main clinical outcome

The main analysis regarding the clinical outcome was the between-group difference in change from baseline to 12 months follow-up in total PDQ-39 summary index score in the mITT population, using a two-group *t*-test. Additionally, a multiple linear regression analysis was performed taking into account the stratifying variable (level of experience of the treatment center) and (if necessary) clinically relevant baseline imbalances. To assess whether the baseline value of the PDQ-39 served as an effect modifier (meaning that the association between intervention and outcome differed according to baseline PDQ-39) an interaction term was used in the regression analysis. In case of a significant interaction term, the analysis was additionally performed in two separate strata: one with patients with a median PDQ-39 or below and the other with patients with a PDQ-39 above median.

Sensitivity analyses

Sensitivity analyses concerning missing data as described in the paragraph “Patient replacement and missing data” were performed in the mITT population. To further assess robustness of the mITT analysis for the main clinical outcome additional sensitivity analyses were performed.

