Additionally, an as-treated analysis was performed to make the effect of treatment switching intelligible for interpretation of the results of the main analysis. Patients could have switched to the other than the allocated treatment either immediately after randomization, without first having had the allocated treatment (these patients were not included in the mITT analysis), or during the follow-up after initial treatment with the allocated therapy. In the analysis of the as-treated population, patients were analyzed according to, if known, the actual treatment they were receiving at the moment of the 12-month visit. In case of add-on treatment with the alternative than the allocated treatment, patients were analyzed in the group of the primary therapy. Missing data were not imputed in this analysis. To evaluate the robustness of the main clinical analysis this was considered the adequate approach while more sophisticated adjustment methods for treatment switching could have led to error in a relatively small RCT.⁷

Finally, to evaluate the effect of protocol violations on the analysis of the main clinical outcome, analysis in the per protocol population was performed.

Analysis of secondary clinical outcomes

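### Table SAP3 counts harms by trial arm without naming its population or linking events to the therapy received, so a second therapy's harms are counted under the allocated one

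*SAP*

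**What the plan says.** Harms are a listed secondary outcome. Under Analysis of secondary clinical outcomes, the SAP states that "All (S)AEs, including death were reported for each treatment arm". The table, headed "Table SAP3. (Serious) Adverse Events", has columns CLI-RCT, DBS-RCT and the two observational groups. Unlike Table SAP2, its heading names no population. The SAP defines no safety set.

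The nearest default is the mITT set. The SAP's RCT analysis section says "The main publication consisted of analyses in the mITT population". The baseline table uses the same two RCT column labels, and there they mean mITT: "For both the RCT mITT population and for the ancillary patient preference population, baseline characteristics were presented in Table SAP1". That set is the one "which included all randomized patients who received the allocated treatment, regardless of continuation of treatment". Appendix I makes patients who refuse the allocated treatment ineligible for it.

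Change of therapy is foreseen in two forms. The as-treated description says "Patients could have switched to the other than the allocated treatment either immediately after randomization, without first having had the allocated treatment", or later, during follow-up; it also provides for add-on treatment. Protocol 7.5 plans to count stopping, crossover and addition of the other treatment. Immediate refusal was seen during the trial: "several patients immediately refused CLI treatment and either chose to be treated with DBS or quitted study participation" (SAP, Synopsis of study protocol development).

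Protocol 8.2.1 records adverse events in RCT patients "from the moment patients undergo visit 1: screening until end of study". Protocol 7.3 allows up to three months between baseline and the start of treatment.

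**The concern.** The two therapies have different characteristic harms, and Table SAP3 is built around them, with rows for gastro-intestinal events, polyneuropathy and cerebral haemorrhage. Such a table will be read as a profile of each therapy. As planned, it is a profile of each allocation, and possibly only of those who accepted it. If a patient allocated to CLI later receives DBS and has a complication of the DBS surgery, the reader sees that complication in the CLI column. The reverse holds for a patient who moves from DBS to CLI. Harms in CLI refusers treated with DBS are either absent from the RCT columns or shown as CLI harms, depending on a population the SAP does not state.

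At stake is a stated secondary objective, the comparison of adverse effects and complications (Protocol 2.2). Protocol section 1 says that little is known about how the two profiles compare, so readers will have little else to check the table against.

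**Working it through.** **1. Where each patient's events go.** Four types of patient, under the two possible readings of Table SAP3:

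| Patient | Event | mITT columns | All randomised, by arm |
|---|---|---|---|
| Allocated CLI, started CLI, later switched to DBS or had it added | DBS-related, after the change | CLI-RCT | CLI-RCT |
| Allocated DBS, started DBS, later switched to CLI or had it added | CLI-related, after the change | DBS-RCT | DBS-RCT |
| Allocated CLI, refused, treated with DBS in the trial | DBS-related | no RCT column | CLI-RCT |
| Any patient, after screening but before any therapy | any | allocated arm, if the patient is in the set | allocated arm |

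The first two rows do not depend on the reading; the third does. Refusers who left the study would have no follow-up in any set and are not part of the point.

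**2. Whether another planned analysis covers it.** The SAP introduces the additional sensitivity analyses as checks on the main clinical outcome, the PDQ-39. The as-treated rule classifies by the therapy in use at the 12-month visit, where known. Applied to harms, it would move a switcher's earlier CLI events to DBS, and it could not place a patient without that visit, such as one who died. So it does not classify events by therapy at the time they occurred.

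**3. The denominator.** Protocol 4.4 plans 33 per arm. This reproduces:
- difference: 34,174 / 120,000 = 0.2848 QALY;
- SD of net health benefit at zero correlation: √(0.35² + (10,000/120,000)²) = 0.3598;
- two-sided 5%, 80% power: 26 per group (exact t-test power at 26 is 0.799);
- 20% dropout: 52 / 0.8 = 65, rounded up to 66, or 33 per arm.

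One patient is 1/33 = 3.0 percentage points.

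**4. Illustration on assumed inputs.** The documents give no number of switchers, treated refusers or events. Assume 33 per arm, all DBS-allocated patients start DBS, r = 1 to 5 CLI refusers are treated with DBS, and s = 1 to 5 patients switch from CLI to DBS. Assume also that each switcher carries the full risk of both therapies.

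- Share of DBS-exposed RCT patients outside the DBS-RCT column under mITT, (r + s)/(33 + r + s): 2/35 = 6% to 10/43 = 23%.
- Risk 30% on each therapy (switcher 1 − 0.7² = 51%). The mITT CLI column shows (31 × 0.30 + 1 × 0.51)/32 = 30.7% at r = s = 1, and (23 × 0.30 + 5 × 0.51)/28 = 33.7% at r = s = 5. DBS shows 30%, so CLI has an apparent excess of 0.7 to 3.7 points where there is none.
- Risks 20% (CLI) and 40% (DBS) (switcher 1 − 0.8 × 0.6 = 52%). The mITT CLI column shows (31 × 0.20 + 0.52)/32 = 21.0% to (23 × 0.20 + 5 × 0.52)/28 = 25.7%. A 20-point gap shows as 19.0 to 14.3 points.
- The same risks with all randomised by arm: (31 × 0.20 + 0.40 + 0.52)/33 = 21.6% to (23 × 0.20 + 5 × 0.40 + 5 × 0.52)/33 = 27.9%. The gap shows as 18.4 to 12.1 points.

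Switching from DBS to CLI would have the mirror effect. Less time on the second therapy would shrink these figures.

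**5. Effect of refusers alone on the DBS percentage.** At an assumed 30% risk, 33 patients give 9.9/33 = 30%. Adding 3 treated refusers at the same risk gives 10.8/36 = 30%. Leaving them out loses events and patients together, so the count falls but the percentage need not.

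**The case against.** Reporting harms by allocated arm is a legitimate treatment-policy view. A complication of DBS given after CLI has failed is a consequence of a CLI-first strategy, and this comparison keeps the protection of randomisation. That stands, and it is why the allocated-arm table should remain.

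The SAP also offers partial safeguards. It plans a line listing, counts of stopping and switching per group, therapy-related rows for death, hospital admission and cerebral haemorrhage, and lines for specifying events. Harms are descriptive, without P-values. A therapy-related haemorrhage in the CLI column would look odd beside the switch counts. This softens the problem without removing it: the related rows do not say which therapy, most event types have no such row, and no field for the therapy received before the event is described.

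Three stronger readings are tempting, and the documents do not support them. First, a reader might conclude that refusers' events are definitely lost. Table SAP3 names no population; mITT is an inference from the default for the main publication and the labels shared with the baseline table. Second, a reader might conclude that the DBS harm rate is understated. Omitting refusers need not lower a percentage, as step 5 shows. Third, a reader might take the observed refusals as evidence that DBS harms will be added to the mITT CLI column. The documents record refusals before CLI was started; they give neither the number nor the direction of switches after starting.

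**Conclusion.** The point holds as a gap in the harms plan. Any event caused by a second therapy after a switch or add-on is shown under the allocated therapy, on either reading of Table SAP3. Events in CLI refusers treated with DBS are either left out of the RCT columns or shown under CLI, depending on a population that is not stated. No planned analysis shows harms by therapy received, and events before any therapy are not set apart.

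Size and direction cannot be computed from the documents. The firm figure is the weight of one patient, about 3 percentage points of 33. The ranges in step 4 rest wholly on assumed counts and risks and show only that a handful of patients can change the picture. The conclusion is not that the allocated-arm table is wrong or that it favours DBS. It is that this table alone does not describe the harms of each therapy, which is how it will be read.

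**What to change.** 1. State the analysis population of Table SAP3 in its heading and in the text.
2. Keep the allocated-arm table as the treatment-policy view.
3. Add a second harms table in all randomised patients who started either therapy. Assign each (S)AE to the therapy or therapies started before it occurred: CLI only, DBS only, or both. Use the onset date where recorded, and otherwise the visit interval in which the event was reported. Give the number of patients exposed in each category, and show events before any therapy in a separate row.

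The cost is SAP wording and one further tabulation from the adverse-event, treatment-course and crossover data already scheduled. It needs no new patients or visits and does not touch the primary analysis. There are two drawbacks. The added table is not a randomised comparison and should be labelled so. And the documents do not say that onset dates are recorded, while Protocol 12.4 schedules adverse events and crossover by visit. Where a switch and an event fall in the same interval, their order may not be recoverable, and such events should be shown as unclassified.
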